7.2.1 Incentives

In appreciation of participants' time all participants will be given a blood pressure cuff at enrollment (about \$20 value), and \$20 at the completion of baseline data collection. Participants will be given \$25 for completing the 6 month outcome assessment and \$30 for completing the 12 month outcome assessment.

Participants randomized to receive facilitated primary care provider appointment scheduling will also be provided transportation for their necessary appointments (about \$15-30/ ride). All participants will be offered facilitated transportation in order to reach outcome assessment appointments. We will track all incentives allocated to participants through the intervention.

Participants may be given a variety of items designed to help promote enthusiasm and obvious contact information for the project including nominal gifts such as pens, a project t-shirt, and other assorted "stuff" with the Reach Out logo. The additional project stuff is pending available funds.

7.3 **Estimation of resources necessary to implement protocol**

We will track the operational aspects of conducting the intervention. This will include: 1) the number of contacts to providers for the research team to schedule the appointments; 2) time required from the research team to schedule follow up; 3) optimal methods to contact participants to schedule follow up. In addition, our research team will actively develop and optimize our manual of procedures and the design of the subsequent follow up study.

8 MANAGEMENT OF ADVERSE EXPERIENCES

Several types of safety issues and serious adverse events may occur in REACH-OUT and participants will be monitored for these regularly throughout the study.

8.1 **Definition of Adverse Event and Serious Adverse Event and Scope of AE reporting**

An adverse event (AE) is any unfavorable and unintended sign, symptom, or disease temporally associated with the use of a medical treatment or procedure regardless of whether it is considered related to the medical treatment or procedure (attribution of unrelated, unlikely, possible, probable, or definite). Each AE is a unique representation of a specific event used for medical documentation and scientific analysis.

A serious adverse event (SAE) is an AE that is fatal or life threatening, is permanently or substantially disabling, requires or prolongs hospitalization, results in a congenital anomaly, requires intervention to prevent permanent impairment or damage, or any event that the treating clinician or internal medical monitor judges to be a significant hazard, contraindication, side effect, or precaution. Reporting serious adverse events (SAEs) are based on the guidelines of the International Conference on Harmonization (ICH).

We will only track adverse events definitely, probably, or possibly related to the intervention.

8.2 Unexpected (Unanticipated) Adverse Event

An unexpected AE is defined as an event that is not anticipated or known to occur as an established risk of either the study intervention or the participant's underlying medical condition. Expected events include, but are not limited to, those specifically identified and described or listed in the study protocol and/or informed consent document.

8.3 Severity of an Adverse Event

‘Severity’ is not the same as ‘serious.’ Serious is based on patient/event outcome or action criteria usually associated with events that pose a threat to a patient’s life or health. The term ‘severe’ is often used to describe the intensity (severity) of a specific event (as in mild, moderate, severe myocardial infarction); the event itself, however, may be of relatively minor medical significance (such as severe headache). Seriousness (not severity) serves as a guide for defining regulatory reporting obligations. Most AEs include clinical criteria that describe patient/event outcomes or indicated interventions to more clearly substantiate seriousness.

8.4 Classification of an Adverse Event

All serious adverse events occurring during study participation will be documented on the AE case report form. Adverse events will be documented using the NCI Common Terminology Criteria for Adverse Events Version 3.0 (CTCAE). The CTCAE provides descriptive terminology that will be used for recording and reporting adverse events that occur. The CTCAE provides a grading (severity) scale for each AE term and AEs are listed alphabetically within categories based on anatomy or pathophysiology. The CTCAE (v 3.0) displays Grades 1-5 with unique clinical descriptions of severity for each AE based on this general guidance:

- Grade 1: Mild AE
- Grade 2: Moderate AE
- Grade 3: Severe AE
- Grade 4: Life-Threatening or Disabling AE
- Grade 5: Death related to AE

Note: Severity is not equivalent to seriousness. A serious adverse event (SAE) would be any event in category 4 or 5, and any event in category 3 that required or prolonged hospitalization.

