8.6 Adverse Event Recording and Reporting

We will only record AEs and SAEs that are possibly, probably, or definitely related to the study interventions.

All AEs reported to the research team and all serious adverse events (SAEs) occurring until participation in the study has ended are recorded on the AE case report form. The PI or Study Coordinator or designee is responsible for entering any and all AEs and SAEs into the database as soon as he/she becomes aware of the event and updating the information (e.g., date of resolution, action taken) in a timely manner. All non-serious AEs must be recorded on the electronic AE CRF within 5 days from the time it was discovered by the study personnel. All SAEs and non-serious AEs must be entered by the end of study for that participant. These will be reported to the IRB per their policy preferences.

The PI is responsible for the monitoring and follow-up of AEs until resolution or the end of study for that participant, and appropriate documentation in the participant research record. In

addition to performing protocol specified follow up, the participating PI must review all previously reported ongoing AEs to evaluate the status. If an AE that was previously reported on the Adverse Event CRF fully resolves and then recurs later, the second occurrence is considered a new AE and a new Adverse Event CRF must be completed. Likewise, if an SAE that was previously reported and subsequently fully resolved later recurs at a level requiring expedited reporting, the SAE must be reported as a new SAE on the Adverse Event CRF.

Upon completion of the study protocol by the participant, premature withdrawal from the study by the participant, or participant's death, all information regarding each AE must be completed, if not already done so.

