9.4 Data Monitoring

The trial does not employ formal efficacy or futility stopping rules. An independent medical monitor (IMM) will be appointed with responsibility to monitor data and oversee participant safety. IMM will be approved by the NIMHD to provide oversight of the trial. The Reach Out IMM will be an expert in the care of hypertension and may either be an emergency medicine physician or a primary care physician. The frequency of IMM meetings will be determined by the IMM, IC, and PI. Given the planned period of data collection we anticipate about 8-10 meetings, in which to advise about study progress and performance, and to make recommendations regarding study continuation and protocol changes.

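### Protocol sections 8.1 and 8.4 give two incompatible definitions of a serious adverse event, and nothing says which one governs

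*Protocol*

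**What the plan says.** Section 8.1 lists what makes an adverse event serious. Besides death, threat to life and lasting disability, it includes an event that "requires or prolongs hospitalization, results in a congenital anomaly, requires intervention to prevent permanent impairment or damage", and "any event that the treating clinician or internal medical monitor judges to be a significant hazard, contraindication, side effect, or precaution". No criterion carries a grade condition.

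Section 8.3 separates intensity from seriousness and says which of the two matters for reporting: "Seriousness (not severity) serves as a guide for defining regulatory reporting obligations".

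Section 8.4 introduces CTCAE grades 1 to 5. It opens its closing remark with "Note: Severity is not equivalent to seriousness", and in the next sentence says that an SAE "would be any event in category 4 or 5, and any event in category 3 that required or prolonged hospitalization".

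On timing, section 8.6 makes staff responsible for entering every AE and SAE in the database as soon as they know of it. It then adds two limits: "All non-serious AEs must be recorded on the electronic AE CRF within 5 days from the time it was discovered", and "All SAEs and non-serious AEs must be entered by the end of study for that participant". Section 8.7, which deals with SAEs, adds no time limit for database entry and leaves reporting to the IRB's own policy.

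**The concern.** A protocol needs one definition of seriousness. Here two people can each follow the protocol and disagree on the same event. Take a grade 2 event, judged related to the intervention, that leads to admission: it is serious under 8.1 and non-serious under 8.4. The 8.4 rule also derives seriousness mainly from grade, directly after saying that the two are different things.

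At stake are the SAE label on the case report form, any count of SAEs given to the IRB or the medical monitor or published with the results, and whatever reporting depends on that label. When few related events are expected, one event classed differently can change the reported SAE count.

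**Working it through.** No arithmetic applies beyond a count. The check sets each criterion in 8.1 against the grade rule in 8.4, using the grade meanings printed in 8.4 (grade 4 is life-threatening or disabling, grade 5 is death).

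| Criterion in 8.1 | Serious under 8.4? | Gap |
|---|---|---|
| Death | Yes, grade 5 | None |
| Threat to life | Yes, grade 4 | None |
| Permanent or substantial disability | Yes, grade 4 | None |
| Admission or longer stay | Grades 3 to 5 only | Grades 1-2 |
| Congenital anomaly | Grades 4-5, or grade 3 if admitted | Grades 1-3 without admission |
| Intervention to avert permanent harm | Grades 4-5, or grade 3 if admitted | Grades 1-3 without admission |
| Judged a significant hazard | Grades 4-5, or grade 3 if admitted | Grades 1-3 without admission |

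The last three rows share a further gap, grade 1-2 with admission, which the admission row already contains. With death and threat to life counted separately, 8.1 has seven criteria. The grade rule covers three fully and four only in part (7 - 3 = 4). A grade 3 event with admission is serious under both rules, so the admission gap is confined to grades 1-2.

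Next, what happens to an event in a gap if staff use 8.4. Under 8.6, related AEs and SAEs go on the same case report form and into the same database. The sentence there on IRB reporting follows one that names both kinds of event. The event is therefore recorded, and it falls under the five-day limit for non-serious events. What it loses is its status as serious, which 8.3 says guides reporting.

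Timing in 8.6, side by side:

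| Rule | Non-serious AE | SAE |
|---|---|---|
| Enter on becoming aware | Applies | Applies |
| Five days from discovery | Applies | Not named |
| End of the participant's study | Applies | Applies |

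The prompt-entry duty covers both kinds of event. The only limit counted in days names non-serious events alone. Section 8.6 also mentions a recurrent SAE at a level that calls for expedited reporting, but sections 8.1 to 8.8 define neither that level nor a time frame.

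**The case against.** The strongest reply is that 8.1 governs on a natural reading. Its heading announces the definition, 8.3 supports it, and the grade sentence sits in a remark about grading. Misclassification then happens only if someone applies 8.4 over 8.1. This stands as a limit: the documents do not show that any event has been misfiled, and a reader who infers that goes beyond them. It does not remove the contradiction, because the 8.4 sentence is worded as a rule and no text ranks it below 8.1.

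The second reply is that hardly any event can be affected, and this largely stands. Sections 8.1 and 8.6 and SAP 2.8 limit recording to events at least possibly related to the intervention. The components are text messages, home blood pressure readings and help with appointments and transport. Section 8.8 anticipates no specific adverse events. Section 11.1.2 stops the intervention elements once a pregnancy is known, which makes the congenital-anomaly case remote. SAP 2.8 tabulates by event type and highest grade, so its listed tables would not change.

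Three stronger readings are tempting and are not supported:

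- *SAEs may be entered as late as the end of follow-up while non-serious events have five days.* The duty to enter events on becoming aware expressly covers SAEs. The end-of-study sentence covers both kinds of event and reads as a completeness check, so an SAE held back for months would breach 8.6.
- *SAEs bypass the medical monitor or would miss the monitor's meetings.* Section 9.4 says "An independent medical monitor (IMM) will be appointed with responsibility to monitor data and oversee participant safety" and does not exclude SAEs from those data. The inference rests on silence. The different title given to the monitor in 8.1 is a matter of wording.
- *SAE status decides whether an event is recorded at all.* Sections 8.4 and 8.7 do speak of recording all SAEs, but 8.6 restricts both AEs and SAEs to related events and puts both on one form.

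**Conclusion.** The contradiction is real and can be read directly from the text: four of the seven criteria in 8.1 are only partly met by the rule in 8.4, and 8.4 departs from the principle stated in 8.3 and in its own note. The consequence is conditional and small. It arises only where staff apply 8.4, it affects the classification, count and reporting of SAEs, and it leaves the primary analysis untouched.

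This rests on two assumptions. The first is that the related-only restriction governs what is recorded. The second is that IRB policy, which is not in these documents, may treat serious and non-serious events differently or set its own deadlines. If it treats them alike, the effect is on labels and counts only.

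The timing point is secondary: SAEs have a prompt-entry duty but no limit in days, whereas non-serious events have both. The change is worth making because it costs almost nothing and the protocol's own principle already points to it.

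**What to change.** 1. Delete the grade-based SAE sentence in 8.4. State that 8.1 is the only definition of an SAE and that CTCAE grades describe severity only.
2. Recheck all recorded adverse events against 8.1 before safety results are reported, and correct any SAE label that was assigned by grade. This step matters most if follow-up is largely complete, as it may be for a protocol at version 14.0, dated August 2022.
3. In 8.6, extend the existing five-day limit to SAEs, alongside the duty to enter events on becoming aware, so that the end-of-study sentence cannot be taken as the limit for SAEs.

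The cost is a short wording amendment and one pass through what should be a small set of recorded events. Slightly more events may be classed as serious. No intervention, visit or analysis model changes.

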8.5 Relationship to Study Treatment

At the time that an AE is reported, the PI is responsible for designating the likelihood that the AE is caused by the study intervention. This determination requires clinical judgment, but for purposes of this study, an algorithm is used to help the investigator report in a manner that is consistent across the trial and done as objectively as possible.

Modified for Reach Out, based upon: Adverse Events Reporting Requirements SOP (NIH-NIAID <http://www.niaid.nih.gov/ncn/sop/adverseevents.htm>, accessed 11-30-04).

Not related: The temporal relationship between treatment exposure and the adverse event is unreasonable or incompatible and/or adverse event is clearly due to extraneous causes (e.g., underlying disease, environment)

Unlikely: May have reasonable or only tenuous temporal relationship to intervention. Must meet both of the following conditions:

- Could readily have been produced by the participant's clinical state, or environmental or other interventions.
- Does not follow known pattern of response to intervention.

Possibly: Must meet any 2 of the 3 following conditions

- Has a reasonable temporal relationship to intervention.
- Could not readily have been produced by the participant's clinical state, environmental, or other interventions.
- Follows a known pattern of response to intervention.

Probably: Must meet all 3 of the following conditions

- Has a reasonable temporal relationship to intervention.
- Could not readily have been produced by the participant's clinical state or have been due to environmental or other interventions.
- Follows a known pattern of response to intervention.

Definitely: Must meet all 3 of the following conditions

- Has a reasonable temporal relationship to intervention.
- Could not possibly have been produced by the participant's clinical state or have been due to environmental or other interventions.

Follows a known pattern of response to intervention.

8.6 Adverse Event Recording and Reporting

We will only record AEs and SAEs that are possibly, probably, or definitely related to the study interventions.

All AEs reported to the research team and all serious adverse events (SAEs) occurring until participation in the study has ended are recorded on the AE case report form. The PI or Study Coordinator or designee is responsible for entering any and all AEs and SAEs into the database as soon as he/she becomes aware of the event and updating the information (e.g., date of resolution, action taken) in a timely manner. All non-serious AEs must be recorded on the electronic AE CRF within 5 days from the time it was discovered by the study personnel. All SAEs and non-serious AEs must be entered by the end of study for that participant. These will be reported to the IRB per their policy preferences.

The PI is responsible for the monitoring and follow-up of AEs until resolution or the end of study for that participant, and appropriate documentation in the participant research record. In

addition to performing protocol specified follow up, the participating PI must review all previously reported ongoing AEs to evaluate the status. If an AE that was previously reported on the Adverse Event CRF fully resolves and then recurs later, the second occurrence is considered a new AE and a new Adverse Event CRF must be completed. Likewise, if an SAE that was previously reported and subsequently fully resolved later recurs at a level requiring expedited reporting, the SAE must be reported as a new SAE on the Adverse Event CRF.

Upon completion of the study protocol by the participant, premature withdrawal from the study by the participant, or participant's death, all information regarding each AE must be completed, if not already done so.

8.7 Serious Adverse Event Recording and Reporting

All Serious Adverse Events (SAEs) occurring during a participant's study participation will be recorded. These will be reported to the IRB per their policy preferences.

8.8 Formal Definitions of Selected or Anticipated Adverse Events and Safety Outcomes

Our team does not anticipate any specific adverse events related to the study intervention.

9 STATISTICAL CONSIDERATIONS

9.1 Data analysis

The primary analysis (aim 1) will fit a linear regression model with the outcome of SBP change (baseline minus 12 months) and main effect-coded binary predictors of healthy behavior texts (yes vs. no), prompted BP self-monitoring frequency (high vs. low), and primary care provider visit scheduling and transportation (active vs. passive). Initial analyses will focus on the main effects. Additional analyses will include all the two-way interactions of the three intervention components (only considering interactions where at least one of the factors in the interaction demonstrates a sufficiently large main effect). As the goal of this exploratory trial is to find interventions and combinations with activity, we will use an alpha level of 0.10 for all main effects and 0.20 for interactions. We plan to include elements meeting that bar for statistical significance in the subsequent multicenter trial. If significant interactions exist (i.e. the combination of facilitated transportation and high frequency home BP monitoring), we plan to implement the combination of elements that has the highest expected reduction in SBP – assuming we achieve significance at the $p=0.1$ (main effects) or 0.2 (interaction) level for the components. In the event of an overall “null” trial, we would examine the expected change in SBP for arm 1, which would be represented by the intercept. If this was significantly greater than 0 at the $p=0.1$ level we would propose a very simple subsequent multi-center trial using only weekly prompted BP self-monitoring.

The main secondary analyses (aim 2) will use time-to event (Cox Proportional Hazards) and logistic regression. For the endpoint of interest, (either time to first primary care visit, or the binary variable indicating attendance at two or more primary care visits within 1 year of randomization), we will fit an adjusted regression model. The main predictor of interest for these models is assignment to the active primary care provider scheduling and transportation arm (50% of all

participants randomized in the trial), while adjusting for the assignment into other groups similar to aim 1 (healthy behavior text messages and prompted BP self-monitoring).

We will conduct additional exploratory analyses using the stratification factors (age, sex, and antihypertensive use) as covariates. As uncertainty exists on the distribution of enrolled participants within these strata (e.g. young men taking antihypertensive medication), we cannot estimate the preliminary statistical power for these exploratory aims. Thus, we will estimate the power based on the strata sizes prior to conducting the exploratory analyses. Interaction terms (e.g. age with behavioral interventions, sex with behavioral interventions, etc.) will be utilized to determine if specific groups respond well to specific intervention elements. Baseline BP may also play an important role. We will examine its impact by dividing the cohort into tertiles. We will repeat the above primary and exploratory modeling within each of the three initial BP strata to determine if there is heterogeneity of effect (e.g. do patients with the highest baseline BPs get the most benefit from the intervention components?). We will similarly assess the impact of the intervention components on the exploratory and process outcomes using linear, Poisson, logistic, or ordinal regression depending on the distributions. In addition, we will conduct longitudinal analyses that include all BP measurements over time (including those by text and at the in-person visits) to assess the temporal profiles of response in the intervention components.

9.2 Endpoints

- Average change in systolic BP from baseline to 12 months
- Time from ED visit to arrival at first primary care visit (in days)
- Attendance at two or more primary care visits within 12 months of randomization

9.3 Sample Size and Accrual

We originally planned to enroll approximately 960 patients into the eligibility phase. From this group, we estimate that 480 participants will report qualifying BPs and will be randomized to one of the eight intervention arms. We anticipate 240 participants will fully complete the 12 month, in person follow up visits.

However, after accruing approximately 400 randomized participants, we noted lower than expected retention at 6 month visits. Therefore, we will adjust the maximum total number of enrollments and randomizations upwards by 50% each. The overall intention is to achieve approximately 240 protocol completers (attendees at 12-month visit). We will continue to monitor accrual and retention in order to achieve this target.

In the work by Collins and others, methods for sample size estimations for factorial design, MOST based interventions, have previously been reported. It is important to note, that the primary hypotheses driven by these designs is not in the pairwise comparisons of each of the interventions, but instead is the overall estimate of the effects of each of the individual intervention components, and their combinations. This smallest standardized effect size of 0.35 corresponds to a BP change of 1 mm Hg and standard deviation of 2.8 mm Hg for each parameter. We believe this is the minimal clinically significant change for each component; and to achieve improvements of 3-4 mm Hg over the course of a year, our chosen regimen for the next phase

would need a component or combination of components to perform better than an expected 1 mm Hg change. For 80% power to detect the smallest main expected effect of 0.35 based on the Collins method of a 3-factor experiment analyzed using a second order model (i.e. main effects and 2-way interactions), we require 196 participants. Assuming 480 randomized participants, and allowing an additional 50% loss to follow up after the eligibility phase, we expect at least 240 participants, exceeding 80% power with an alpha level of 0.10 (inflated to reduce likelihood of dismissing active components with modest BP reducing effect) – we used the FactorialPower-Plan SAS macro to calculate power. For the secondary analyses, considering an alpha of 0.05 and a baseline proportion attending 2 or more primary care provider visits within one year of 40%, with a total sample size of 240 evenly distributed between the active appointment scheduling and passive appointment, we have 87% power to detect an increase to 60% attending 2 or more visits. The time to event analysis (considering an alpha of 0.05, power of 99%, and 240 participants enrolled over 720 days, followed for 30 days) can detect a change from 20% of participants in the non-facilitated group to 20.4% of participants in the facilitated group. This high power allows ample room to adjust for covariates and loss to follow up. Sample size calculations for secondary outcomes performed with STPLAN (version 4.5).

The challenges of recruiting racial minorities and people with socioeconomic disadvantage for clinical research studies are well documented. Reach Out participant recruitment will be facilitated by several factors: 1) the study is no more than minimal risk; 2) culturally and community sensitive recruitment materials were created using a CBPR approach; 3) enrollment in an urban, safety net ED; and 4) monetary incentives.

